3.1 Study Design

This study is a randomized controlled, intervention-based clinical trial. Eligible patients were randomly assigned in a 1:1 ratio to either the ta-VNS group or the sham stimulation group. The primary endpoint was the incidence of acute kidney injury (AKI) within 7 days postoperatively. The objective of this study was to evaluate the efficacy and safety of continuous 6-day perioperative ta-VNS intervention in reducing the incidence of AKI following cardiac surgery under cardiopulmonary bypass (CPB).

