3.3.2.3 Basic Clinical Indicators

Prior to randomization of patients, trained investigators collected the following baseline data. All measurements were based on the most recent test conducted after hospital admission and prior to surgery, and must be completed before randomization.

Demography and anthropometry: age, gender, height, weight, body mass index (BMI), ASA classification.

Cardiac function and risk scoring: NYHA cardiac function classification, left ventricular ejection fraction, EuroSCORE II score, Cleveland Clinic score, history of cardiac surgery, recent myocardial infarction (MI) history (<3 months).

Clinical history and comorbidities: history of hypertension, diabetes mellitus, chronic kidney disease, cerebrovascular disease, peripheral vascular disease, chronic obstructive pulmonary disease, hepatic insufficiency (Child-Pugh classification), smoking history, and alcohol consumption history.

Preoperative medication history: Record medications used within 24 hours prior to randomization that cannot be safely discontinued, including RAS inhibitors, β -blockers, calcium channel blockers, diuretics, statins, antiplatelet agents, oral hypoglycemic agents or insulin, and nonsteroidal anti-inflammatory drugs (within 48 hours before surgery).

Baseline laboratory tests: serum creatinine, eGFR (CKD-EPI formula), blood urea nitrogen, hemoglobin, platelet count, albumin, myocardial troponin I, NT-proBNP, and high-sensitivity C-reactive protein.

Surgical parameters: Type of surgery, surgical urgency, extracorporeal circulation time, aortic cross-clamping duration, minimum nasopharyngeal temperature, intraoperative red blood cell transfusion volume, intraoperative urine output, and use of vasoactive drugs during surgery.

Previous intervention history: Whether the participant received vagus nerve stimulation, auricular acupuncture, transcutaneous electrical stimulation therapy, or participated in other clinical studies within 1 month prior to enrollment.

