3.3.3 Statistical Analysis Plan

All data in this study were processed using SPSS 26.0 and R 4.3.0 software.

For continuous variables, the Shapiro-Wilk normality test is first performed. Variables conforming to normal distribution are expressed as "mean \pm standard deviation," with intergroup comparisons conducted using the independent samples t-test. Variables not conforming to normal distribution are represented by median values (25th and 75th percentiles), and intergroup comparisons are performed using the Mann-Whitney U rank-sum test. Categorical variables are presented as frequencies (percentages), with intergroup comparisons analyzed using the χ^2 test. If theoretical frequencies do not meet the test requirements, the Fisher exact probability method must be employed.

The primary endpoint of this study was the incidence of AKI within 7 days postoperatively, analyzed based on the intention-to-treat principle. Kaplan-Meier curves were constructed to plot the cumulative incidence of AKI within 7 days postoperatively for both groups, with intergroup comparisons performed using the log-rank test. The Cox proportional hazards regression model was employed to estimate the hazard ratio (HR) and its 95% confidence interval for the ta-VNS group versus the sham stimulation group. A single-factor COX regression model incorporating only grouping variables was first fitted to estimate the crude effect, followed by a multivariate

COX regression model that adjusted for preoperative eGFR (<90 vs. ≥ 90 mL/min/1.73 m²), diabetes history (present vs. absent), left ventricular ejection fraction (<35% vs. $\geq 35\%$), and surgical type (high-risk group [valve and coronary artery combined/aortic surgery] vs. low-risk group [valve and septal repair]) as covariates. Under the random missingness assumption, imputation models were constructed based on covariates related to outcomes and missingness states, generating 20 imputed datasets for analysis, with results combined according to the Rubin rule. Under the non-random missingness assumption (all missing values in the ta-VNS group were AKI, while all missing values in the sham stimulation group were non-AKI), intergroup comparisons were re-evaluated.

The severity of AKI was analyzed using multivariate ordered logistic regression, adjusting for the same covariates as in the primary analysis and testing the proportional hazards assumption. Results were reported as odds ratios (OR) and their 95% confidence intervals (CI).

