3.4 Research Flowchart

IV. Sample Size Calculation

The sample size for this study was estimated based on preliminary experimental results from our research center. In the pilot study, the incidence rates of CPB-associated AKI in the ta-VNS group and sham stimulation group were 17.1% and 37.9%, respectively. With a significance level of $\alpha = 0.05$ (bilateral) and a power of $1 - \beta = 0.80$, calculated using G*Power software (version 3.1.9.7), 68 patients were required in each group. Considering a 10% dropout rate, a total of 152 patients were enrolled in this study, with 76 patients in each group.

V. Data Management and Confidentiality

Only investigators authorized by the principal investigator are permitted to access or analyze data. Computer systems used for data management must be password-protected, and paper documentation must be locked.

All information related to the subject's identity is kept confidential, and such information shall not be disclosed beyond the scope permitted by applicable laws and/or regulations.

VI. Informed Consent

Prior to enrollment in this study, the investigator responsible for obtaining informed consent must provide each participant with a comprehensive written explanation regarding the study's objectives, nature, procedures, potential benefits, and risks. Participants should be informed of their right to withdraw from the study at any time. Before enrollment, each participant must be fully informed and given sufficient time to consider participation. Enrollment is permitted only after voluntary participation and signing of the informed consent form.

The vulnerable groups potentially involved in this study include elderly individuals and illiterate persons. If the subject is unable to read or sign the informed consent form due to lack of capacity for action, their guardian must act as proxy for the informed consent process and sign the document. If the subject lacks the ability to read the informed consent form (e.g., illiteracy), a witness must observe the informed consent process and sign the consent form.

VII. Adverse Events and Related Management Measures

ta-VNS is a selective, non-invasive, and low-risk effective VNS strategy. The primary

adverse events include pain, influenza-like symptoms, and local skin discomfort, which resolve immediately after cessation of stimulation. To date, no literature has reported serious adverse events associated with this procedure.

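### The adjusted Cox and severity models dichotomise eGFR and LVEF although both are collected uncategorised; this costs some prognostic information and, if effects are roughly linear, about 0 to 5 points of power

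*Combined protocol and SAP*

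**What the plan says.** Section 3.3.3 introduces the endpoint as follows: "The primary endpoint of this study was the incidence of AKI within 7 days postoperatively, analyzed based on the intention-to-treat principle". It then plans a log-rank test, a Cox model with treatment group alone, and a Cox model with four two-level covariates: eGFR below 90 or not, "diabetes history (present vs. absent), left ventricular ejection fraction (<35"% or not), and surgical type in two risk groups. The ordinal logistic model for AKI severity takes the same covariates and refers to them as those of the primary analysis. The subgroup paragraph of the same section uses the same two cuts.

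Section 3.3.2.3 lists the baseline variables without categories: "NYHA cardiac function classification, left ventricular ejection fraction, EuroSCORE II score" and "serum creatinine, eGFR (CKD-EPI formula"). Section 3.2.1 requires eGFR of at least 60 and NYHA class I-III, and sets no LVEF limit. The documents give no LVEF distribution, no expected share below 35%, and no reason for using cuts in the adjustment models.

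**The concern.** A subgroup plot needs categories; covariate adjustment does not. A two-level factor treats an eGFR of 61 and one of 89 as the same, and likewise an LVEF of 36% and one of 65%. Prognostic information that was paid for at data collection is dropped.

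In a Cox model, leaving out prognostic information moves the estimated treatment log HR towards zero. That costs the adjusted test some power. A cut in the tail of LVEF could also leave a category with very few AKI events, so that its coefficient is unstable or cannot be estimated. The plan states no fallback for that case.

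**Working it through.** **Inputs from the documents.** Allocation: "randomly assigned in a 1:1 ratio" (section 3.1). Section IV, Sample Size Calculation, gives pilot AKI rates in the "ta-VNS group and sham stimulation group were 17.1% and 37.9%, respectively", two-sided alpha 0.05, power 0.80, "68 patients were required in each group", 10% dropout and 152 patients in total (76 per arm).

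**Plan's own figure.** With unpooled variance, n = (1.960 + 0.842)² × (0.171×0.829 + 0.379×0.621) / 0.208² = 7.849 × 0.3771 / 0.04326 = 68.4, so 69 per arm. This is within one patient of 68. The arcsine form gives 70. Other formulas give more (pooled 72, continuity-corrected 81). Dropout: 68/0.9 = 75.6, so 76 per arm, as stated.

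**Events and parameters.** 68 × (0.171 + 0.379) = 37.4 and 76 × 0.55 = 41.8 events. Treatment plus four covariates makes 5 parameters, or 7.5 to 8.4 events per parameter. Linear continuous terms leave that count unchanged.

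**Information kept by a cut.** For a normal covariate with a linear effect, the share of explained variance kept is φ(z)²/[p(1−p)], where p is the share on one side of the cut:
- p = 0.50: 0.3989²/0.25 = 0.64
- p = 0.10: 0.1755²/0.09 = 0.34
- p = 0.05: 0.1031²/0.0475 = 0.22

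Normality is an assumption. Entry at eGFR ≥ 60 truncates that variable, so these figures are only approximate for eGFR.

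**Effect on the treatment comparison.** Cox simulation with 76 per arm, risks calibrated to 17.1% and 37.9%, normal covariates with linear effects, eGFR cut at its median, other covariates omitted, 2,000 runs per cell (Monte Carlo error about 0.8 points). The prognostic strengths and LVEF shares are assumptions. Power with cuts versus continuous:

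| log HR per SD | 5% below LVEF 35% | 10% below LVEF 35% |
|---|---|---|
| 0.2 | 83.4 vs 83.2% | 82.6 vs 83.0% |
| 0.4 | 83.0 vs 86.3% | 85.0 vs 86.4% |
| 0.6 | 85.3 vs 89.8% | 87.6 vs 91.6% |

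At 0.6 and 5%, the mean treatment log HR was −1.015 with cuts and −1.083 continuous. In a separate simulation (8% below 35%, conditional HR 0.394, 1,500 runs) the median standard errors were 0.342 vs 0.342, 0.349 vs 0.350 and 0.359 vs 0.361 at 0.2, 0.4 and 0.6. The gain therefore comes from less attenuation, not from a smaller standard error.

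**Possible sparsity.** Pooled AKI risk is (0.171 + 0.379)/2 = 0.275. For an assumed share q below 35%, with the same risk in both LVEF groups, patients = 152q, events = 152q × 0.275, and P(no event in the category) = (1 − 0.275q)^152:

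| q | Patients | Events | P(no event) |
|---|---|---|---|
| 2% | 3.0 | 0.8 | 43% |
| 5% | 7.6 | 2.1 | 12% |
| 10% | 15.2 | 4.2 | 1.4% |
| 20% | 30.4 | 8.4 | about 0% |

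If low LVEF raises risk, the category holds more events: 4.4 to 6.0 on average at q = 8% under the linear effects above.

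**The case against.** Three stronger readings are tempting.

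- A reader might infer that the cut creates a sparse LVEF category. The documents do not show this. They give no LVEF distribution, and at a 20% share the category would hold about 8 events. Sparsity and power loss are also strongest under opposite assumptions: the low event counts take LVEF as non-prognostic, whereas the power gain needs it to be prognostic.
- A reader might infer that the treatment effect is estimated less precisely. The standard errors above do not differ materially. Even in the few runs with no event in the LVEF category, the treatment estimate stayed finite, with a median standard error of 0.35 to 0.37. What becomes unstable is a nuisance coefficient.
- A reader might infer that the primary analysis as such is compromised. The plan does not expressly name which of the log-rank test, crude Cox model and adjusted Cox model is primary. The severity paragraph only implies that it is the adjusted one, and the other two do not use these covariates. Treatment is randomised and the cuts are prespecified, so coding them this way introduces no confounding.

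The best remaining objection is that simulations built on linear effects must favour linear coding. That stands. When the outcome was generated with a true step at the cut, the order reversed. The loss from linear coding was about 0 to 2 points in one set of runs. In another it was 2.2 points (78.9 vs 76.7%) and, in the strongest step scenario, 9.4 points (73.5 vs 64.1%). The documents do not say which shape holds. None of this supplies a reason for discarding the measured values, but it does mean that the cut version should still be reported.

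**Conclusion.** The point holds as a low-cost improvement and not as a flaw in validity. The adjusted Cox and severity models discard prognostic information without a stated reason. The consequence is a slightly attenuated adjusted log HR and about 0 to 5 points of lost power if effects are roughly linear. With weak prognosis (0.2 per SD) the difference is within simulation error. Instability of the LVEF coefficient is a risk, material if about 5% of patients or fewer fall below 35% and not clearly so at 20%; the treatment estimate is little affected.

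These sizes rest on assumed covariate distributions, prognostic strengths and LVEF shares, none of which the documents give. Type I error, the sample size of 152, the log-rank test and the crude Cox model do not change.

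**What to change.** In section 3.3.3, state that preoperative eGFR and LVEF enter the adjusted Cox model and the ordinal severity model as continuous terms. Choose the form before unblinding: linear, or a low-df spline with knots fixed in advance. Linear terms keep 5 parameters. A spline with 2 df for each variable would make 7, or 37.4/7 = 5.3 to 41.8/7 = 6.0 events per parameter, so there is little room for anything more flexible.

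Report the model with the present cuts as a sensitivity analysis, and keep the cut-offs for the subgroup forest plot. State what will be done if the LVEF category has no events in that sensitivity analysis.

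The cost is a change of SAP wording; no new data or patients are needed. The downside is that a linear term can lose a point or two of power if the true effect is a threshold at the stated cut, and more if the step is very large.

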3.3.2.2 Secondary Outcomes

1) Severity of AKI

Within 7 days postoperatively, the postoperative AKI classification was assessed according to KDIGO criteria based on AKI severity (KDIGO staging: Stage 1/2/3):

Stage 1: Serum creatinine elevation ≥ 0.3 mg/dl or 1.5 – 1.9 times the baseline value, or urine output < 0.5 mL/(kg · h) for 6 – 12 hours;

Stage 2: Serum creatinine levels increased 2.0 – 2.9-fold, or urine output < 0.5 mL/(kg · h) for ≥ 12 hours;

Stage 3: Serum creatinine elevation ≥ 3.0 mg/dl, or ≥ 3 times the baseline value, or urine output < 0.3 mL/(kg · h) for ≥ 24 hours, or requiring RRT.

The AKI severity grading was determined by the highest KDIGO stage achieved within 7 days postoperatively.

2) Renal replacement therapy

The proportion and duration of acute RRT required during hospitalization.

3) Renal function recovery

In patients with AKI, those who still meet AKI criteria on postoperative day 7 were defined as having persistent AKI. The time from diagnosis to the first recovery of serum creatinine to within 1.5 times the baseline level without the need for RRT was calculated as the creatinine recovery time.

4) Long-term renal function

Serum creatinine and eGFR at 30 days postoperatively.

5) Autonomic nervous function

5-minute electrocardiogram (ECG) signals were collected preoperatively and at 24 hours, 48 hours, and 72 hours postoperatively, with heart rate variability (HRV) analyzed using Kubios HRV software.

6) Early recovery quality

Postoperative early recovery quality was systematically evaluated from multiple dimensions. Mechanical ventilation duration was defined as the time from the first successful extubation after surgery. The vasoactive drug index was calculated daily within 7 days postoperatively, with peak values and mean values recorded separately. Delirium incidence was assessed daily using either

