Unless otherwise specified, all tests were conducted as two-tailed tests with a significance level set at $\alpha = 0.05$, meaning that differences were considered statistically significant when $P < 0.05$.

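### The AKI severity model is an ordered logistic regression, but the plan names proportional hazards, not proportional odds, as the assumption to test, so the basis of its single OR goes unchecked

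*Combined protocol and SAP*

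**What the plan says.** Section 3.3.2.2 defines the outcome: "The AKI severity grading was determined by the highest KDIGO stage achieved within 7 days postoperatively". Each patient therefore contributes one ordered category.

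Section 3.3.3 gives the model: "The severity of AKI was analyzed using multivariate ordered logistic regression", with odds ratios and 95% CIs as the reported result. The same sentence adds the phrase "adjusting for the same covariates as in the primary analysis and testing the proportional hazards assumption". No test is named, and nothing is said about what follows if the assumption fails. Proportional odds (parallel lines) is not mentioned anywhere in the documents.

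The same section does contain a hazards model, for the primary endpoint: "The Cox proportional hazards regression model was employed to estimate the hazard ratio (HR) and its 95% confidence interval". No proportional-hazards check is stated for it, nor for the optional Cox models for complications and mortality later in the section.

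**The concern.** A standard ordered logistic model with one group coefficient applies the same OR at every cut-point: any AKI against none, Stage 2 or higher against less, and Stage 3 against less. That is the proportional-odds assumption. Proportional hazards is a different property, the constancy of a hazard ratio over time. It has no meaning for a worst-stage outcome without a time axis. As written, the severity OR carries no relevant check.

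What is at stake is how the result is read. Severity is named in the research objective (section II) and is the first-listed secondary outcome. If ta-VNS prevented mainly mild, Stage 1 AKI, one OR well below 1 would invite the claim that severe AKI is reduced as well.

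**Working it through.** **Inputs from the documents.** The AKI rates come from section IV: "in the ta-VNS group and sham stimulation group were 17.1% and 37.9%, respectively". Group size is 76 per arm (section IV), and tests are two-sided at 0.05 (section 3.3.3). The plan states no figure for severity, so there is none to reproduce.

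**Inputs assumed.** The documents give no split by stage. Two were used:
- Split A: sham none/1/2/3 = 62.1/25/9/3.9%.
- Split B: sham AKI divided 80/15/5% over Stages 1/2/3.

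Covariates were left out.

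**Step 1: OR at the first cut-point.**
Odds with ta-VNS: 0.171/0.829 = 0.206. Odds with sham: 0.379/0.621 = 0.610. OR = 0.206/0.610 = 0.34.

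**Step 2: what one OR implies higher up (split B).**
Sham Stage 2 or higher: 0.379 × 0.20 = 0.0758, odds 0.0758/0.9242 = 0.0820. Multiplying by 0.338 gives odds 0.0277, a risk of 0.0277/1.0277 = 2.7%. A common OR of 0.34 thus asserts a fall from 7.6% to 2.7% at Stage 2 or higher. With a 60/25/15 split the same arithmetic gives 15.2% to 5.7%.

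**Step 3: benefit confined to Stage 1.**
Under split A, the ta-VNS arm becomes 82.9/4.2/9/3.9%. Stage 2 or higher is 12.9% in both arms and Stage 3 is 3.9% in both, so the cut-point ORs are 0.34, 1.0 and 1.0. Fitting the common-OR model to simulated trials (600 per scenario) gives:
- a common OR of about 0.40 under split A and about 0.36 under split B;
- significance in favour of ta-VNS in roughly 70% of trials (A) and 77% (B).

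**Step 4: would a correctly named test catch it?**
Rejection rate of a likelihood-ratio test of proportional odds, with any-AKI OR 0.34 throughout:

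| True OR at Stage 2 or higher | Split A | Split B |
|---|---|---|
| 1.0 (benefit at Stage 1 only) | 76–79% | 43–45% |
| 0.67 | 27–29% | 19% |
| 0.5 | 12% | 10% |

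The ranges are repeated runs and reflect simulation error. When proportional odds holds, the test rejects in about 5%. The figures describe these two splits and are not bounds: a larger share of Stages 2–3 would raise power.

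**Step 5: who is in the model.**
The plan does not say whether no AKI is the lowest category. If only patients with AKI were modelled, about 76 × (0.171 + 0.379) = 42 patients are expected, and power in the split A, Stage-1-only case falls to 18%.

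**Step 6: precision of the higher cut-points.**
Under split A about 76 × 0.129 = 9.8 patients per arm reach Stage 2 or higher. For a true OR of 1, the standard error of the log OR is √(2/9.8 + 2/66.2) = 0.48, an approximate 95% CI of 0.39 to 2.6. Stage 3, with 76 × 0.039 = 3.0 per arm, is less precise still.

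**The case against.** The strongest reply is that this is one wrong word. The phrase sits in a sentence about ordered logistic regression and is followed by odds ratios. The text has other rendering slips, such as the garbled names for the GEE working correlation and for KDIGO. That is the likely explanation, and a reader who infers that the sponsor deliberately chose the wrong test goes further than the documents allow. What remains is that the plan is the prespecified record, nothing in it corrects the word, and even the corrected word comes with no named test and no reporting rule.

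The harm is also partly mitigated. Section 3.3.3 presents categorical variables as counts and percentages, so stage counts by arm should be visible, and RRT and persistent AKI are compared separately. Without proportional odds the common OR can still be read as an average over cut-points. This stands, and it limits the size of the point. It does not supply effect estimates by cut-point.

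Two stronger readings are tempting. One is that the plan will generate false alarms or missed violations at some measurable rate by testing proportional hazards on severity. That test cannot be run on an outcome with no time axis. Any such rate would describe time to AKI onset, a different outcome, so it is not a consequence of the plan. The other is that a proportional-odds test alone would cure the problem. The table shows that it would often miss a real violation.

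**Conclusion.** The point holds as an error in the stated rule for one secondary outcome: the assumption named is not the one on which the severity OR rests. It should be corrected, but it does not touch the primary comparison or the sample size.

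Its size depends on the pattern of effect. If benefit were confined to Stage 1, a common OR of about 0.36 to 0.40 would be significant in roughly 70 to 77% of trials with no effect at Stages 2–3. A proportional-odds test would detect the departures examined with about 10 to 79% power. These figures rest on the design AKI rates, 76 per arm, assumed stage splits, no AKI as the lowest category, and no covariates. Stage-1-only benefit is a strong departure chosen to illustrate the risk; the documents give no reason to expect it in particular.

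The missing proportional-hazards check on the primary Cox model is a real but separate and secondary gap. No size has been worked out for it here.

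**What to change.** In section 3.3.3, in the sentence on AKI severity:
- replace proportional hazards with proportional odds for the group term, and name the test (likelihood-ratio or Brant);
- state that ORs at Stage 1 or higher, Stage 2 or higher, and Stage 3, each with a 95% CI, are reported beside the common OR whatever the test result;
- state that no AKI is the lowest category, which the Stage 1 or higher cut-point requires.

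A rule that switches to a partial proportional-odds model when the test rejects is not recommended. It would choose the model by a pre-test with low power, and reporting the cut-point ORs in every case makes it unnecessary.

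As a secondary point, attach a proportional-hazards check (scaled Schoenfeld residuals) to the primary Cox model.

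The cost is a few sentences and a few lines of code, with no new data and no change to the sample size. The drawback is that the higher-stage ORs will be imprecise, and the report should say so. The wording should be settled before unblinding.
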